### LIST OF ABBREVIATIONS

AE Adverse Event

Al Associate Investigator
BPI Brief Pain Inventory

BNF British National Formulary

CI Chief Investigator
CRF Case Report Form

CRN Clinical Research Network

CTU Clinical Trials Unit
GCP Good Clinical Practice

GDPR General Data Protection Regulation

GP General Practitioner

ID Identification Detail number

IP Intellectual Property

HRA Health Research Authority

HSCR Health and Social Care Research Policy

ISRCTN International Standard Randomised Controlled Trials Number

MED Morphine Equivalent Dose MRR Medical Record Review

NPT Normalisation Process Theory

PAG Patient Advisory Group
PCN Primary Care Network

PIL Participant Information Leaflet

PPIE Patient and Public Involvement and Engagement

PSC Programme Steering Committee

RCT Randomised Control Trial
REC Research Ethics Committee
SAE Serious Adverse Event

SMF Study Master File

SMG Study Management Group
SOP Standard Operating Procedure
TDF Theoretical Domains Framework

TFA Theoretical Framework of Acceptability

# **STUDY SUMMARY**

Study Title	persistent Pain led by clin	of patients taking O pioid M edicines long-term for nical P harmacists in primary care T eams domised Feasibility Study with mixed methods					
Internal Ref. Number (or short title)	PROMPPT FS						
Patient facing title / ACRONYM	Management of Opioids	Management of Opioids and Persistent Pain (MOPP) Study					
Study Design	Single arm, non-randomi evaluation	sed feasibility study with mixed methods process					
Intervention	•	cist-led review of patients taking opioid medicines orating, where appropriate, support to reduce ge persistent pain.					
Study Participants	analgesic for persistent p	Adults aged ≥ 18 years regularly prescribed any opioid-containing analgesic for persistent pain for ≥ 6 months with a prescription dispensed within the previous 2 months					
Planned Sample Size	4 GP practices						
	80 patient participants						
	Process evaluation (MOPP 2 study)						
	8 consultations audio-recorded across the participating practices (aiming for 2 per participating practice)						
	15 patient participants interviewed						
	4 clinical pharmacists interviewed (1 per participating practice)						
	4 GPs interviewed (1 per	4 GPs interviewed (1 per participating practice)					
Treatment duration	Initial clinical pharmacist	consultation will last around 30 minutes					
	Follow-up arranged acco	rding to clinical need					
Follow up duration	p duration 3 months						
Planned Study Period	od 16 months						
Primary Objectives		Outcome Measures					
To determine:							
the proportion schedul	recruitment of eligible patients, scheduling and attending clinical pointments and retention to 3-p.  • Proportion of patients eligible (out of all GP registered patients) to be mailed a study invitation.						

	
 
Proportion of patients returning a baseline questionnaire (out of those mailed a study invitation).
 

	
 
Proportion of participants attending the initial PROMPPT consultation with the clinical pharmacist (out of those who returned the baseline questionnaire).
 

	Proportion of participants who have at least one follow-up appointment scheduled (out of those who attend the initial consultation).
	Proportion of participants who fail to attend one or more scheduled follow-up appointments (out of those who are scheduled a follow-up following the initial consultation).
	
 
Proportion of participants returning a 3-month follow-up questionnaire (out of those consenting to complete questionnaires at baseline).
 

2. Completeness of data collection.	Missing data rates will be calculated for each outcome measure in the baseline and follow-up self-report questionnaires at each data collection time-point (baseline and 3-month).
3. Fidelity of intervention delivery per protocol.	
 
Proportion of times that use of each intervention component is recorded in intervention case report forms (CRFs).
 
Proportion of patients being treated perprotocol (out of all patients who attended the initial clinical pharmacist appointment).
 
Findings from qualitative analysis of observed/audio-recorded consultations.
 

Suitability of a self-reported pain medicines use questionnaire to calculate mean daily morphine equivalent dose.	
 
Completeness of response to pain medicines use questionnaire.
 
Comparison of average daily morphine equivalent dose (MED) calculated using data from self-report questionnaires with MED calculated using prescription data from electronic medical records at baseline and 3-month follow-up.
 

5. Suitability of the health resource use questionnaire for use in a future health economic evaluation.	Rate and completeness of response to healthcare resource use and productivity questionnaire.
6. Barriers to and facilitators of successful delivery of the intervention.	
 
Findings from observed/audio-recorded consultations.
 
Findings from interviews with patients, clinical pharmacists and GPs.
 

 
The acceptability and credibility of the intervention to patients.
 
	
 
Responses to the Acceptability Questionnaire.
 
Findings from interviews with patients.
 

8. Acceptability of the intervention and training to clinical pharmacists and GPs, and the feasibility of delivering the intervention in general practice.	Findings from interviews with clinical pharmacists and GPs.

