#### Health economic evaluation

The EQ-5D-5L is a generic measure of health related quality of life that provides a single index value for health status that will allow calculation of Quality-Adjusted Life Years (QALYs) in the health economic evaluation nested in a proposed future main trial. Respondents rate their degree of impairment in five health domains (mobility, self-care, usual activities, pain/discomfort, anxiety/depression) on a 5-point scale (no problems, slight problems, moderate problems, severe problems and extreme problems).

A patient self-report questionnaire (developed for the study) will be used to collect relevant healthcare resource use data, including the use of NHS and private health care, over the counter purchases and information on both time off work and presenteeism. The focus will be on persistent pain-related healthcare resource use and healthcare resource use due to opioid-related side effects. Questions will request information regarding primary care visits, visits to other health care professionals, tests and investigations, opioid prescriptions, treatment (e.g. injections), secondary care consultations, inpatient stays and surgery during the previous 3

months. Data on broader health care costs will also be collected, related to out of pocket costs (e.g. over the counter medications such as laxatives) and private health care. Information on time off work, occupation, typical work activities and the nature of their employment (full time or part time) will also be requested and the Single-Item Presenteeism Question from the Work Productivity and Activity Impairment Questionnaire will be used to estimate presenteeism.

Preliminary resource use data will also be collected regarding delivery of the PROMPPT intervention, including clinical pharmacist appointments (face to face and telephone) and GP input, to refine data collection processes in a future main trial. Opioid prescription information will also be available through medical record review (see 5.3.3).

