### 5.3.3 Medical Record Review (MRR)

Full general practice medical records of consenting participants will be accessed and extracted and securely transferred to the study team to obtain information on consultations, prescriptions and associated aspects in the medical record, for the duration of the study requirements.

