#### 6.2.6 Health economic evaluation

A formal health economic evaluation will not be conducted in this feasibility study.

To assess the feasibility of the proposed health economic evaluation for the main trial, we will assess the level of completion of the EQ-5D-5L questionnaire at baseline and 3 months, and the level of completion and suitability of the patient resource use questionnaire at 3 months.

Overall response rates for each questionnaire will be calculated. Within questionnaire completion rates will also be calculated in order to assess the level of completion of specific questions. Assessment of appropriateness of completion will also be undertaken, with questions to be refined as necessary.

Data on opioid prescriptions and use will be available from patient self-report questionnaires and medical record review. This will allow comparison of the two data sources to determine the final method of data collection on opioids for the economic evaluation within the definitive trial.

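### Objective 5 judges the resource-use questionnaire by return and completion, which cannot show whether the primary-care contacts it reports are accurate

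*Protocol*

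**What the plan says.** The Study Summary states objective 5 as "Suitability of the health resource use questionnaire for use in a future health economic evaluation" and lists one outcome for it: "Rate and completeness of response to healthcare resource use and productivity questionnaire".

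Section 6.2.6 rules out a formal economic evaluation in this study. For the questionnaire it plans to assess "the level of completion and suitability of the patient resource use questionnaire at 3 months", overall response rates and within-questionnaire completion. It then adds: "Assessment of appropriateness of completion will also be undertaken, with questions to be refined as necessary". Neither suitability nor appropriateness is given a criterion.

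Section 5.3.1 (Health economic evaluation) says the questionnaire was developed for this study and focuses on use related to persistent pain or opioid side effects. On content it says: "Questions will request information regarding primary care visits, visits to other health care professionals, tests and investigations, opioid prescriptions". The list continues through "secondary care consultations, inpatient stays and surgery during the previous 3" months. The same section separately collects resource use for delivering the intervention, including clinical pharmacist appointments and GP input.

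Section 5.3.3 has the full GP records of consenting participants extracted "to obtain information on consultations, prescriptions and associated aspects in the medical record". Section 6.2.6 uses self-report and records together for opioids: "This will allow comparison of the two data sources to determine the final method of data collection on opioids for the economic evaluation". No corresponding use of the consultation data appears in section 6.

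**The concern.** Completion and accuracy are different properties of a recall questionnaire. A participant who had three visits and reports one returns a form as complete as someone who reports all three. An instrument assessed only on return and completion could be called suitable and carried into the main-trial cost analysis with unknown error in its contact counts.

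This study is the natural place to look. The protocol cites no validation of the questionnaire, and secondary objective 3 (section 3.2) is to refine the self-report questionnaires for the main trial. For the neighbouring objective 4, the pain medicines questionnaire is judged both by completeness and by comparison with records. Objective 5 asks about suitability too, but has only the first of these two checks.

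**Working it through.** The plan states no figure on this point, so the check is mainly a comparison of sections, followed by what the proposed comparison could deliver.

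**1. What each planned measure responds to.**
- Response rate: whether a form came back.
- Item completion: whether each question has an answer.
- Appropriateness of completion and suitability (6.2.6): undefined. On a natural reading the former concerns how questions were answered. No outside source is named that could show a wrong count.

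**2. Illustration that completeness is blind to recall error.** Assume full return, full item completion and a true mean of 3 visits, each recalled with probability r. Reported mean = 3 x r.
- r = 0.9: 2.7 (10% low)
- r = 0.8: 2.4 (20% low)
- r = 0.6: 1.8 (40% low)

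The objective 5 measure is 100% in every row. The values of r are assumptions. They show that the measure does not move, not that such losses will occur.

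**3. What the records can and cannot show.** The questionnaire focuses on pain-related and side-effect-related use, while the extracted records are full GP records. A participant with three recorded consultations, one of them for pain, who correctly reports one, shows the same 1-against-3 gap as one who forgot two pain visits. All-cause counts therefore cannot isolate forgetting. They give an upper bound on the pain-related contacts held in the GP record. PROMPPT pharmacist appointments avoid this problem because they are pain-specific by design and are recorded as intervention resource use.

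**4. Number of pairs.** Inputs from section 6.1: 80 participants and a 3-month follow-up rate of around 75%. Pairs = 80 x 0.75 = 60 at most, because record access is a listed consent item (section 5.1.2, Consent to participate). If 80% or 70% of these allow access (assumed), pairs = 60 x 0.80 = 48 or 60 x 0.70 = 42.

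**5. Precision of the mean paired difference.** 95% half-width = 1.96 x SD / √n. The SD of the differences is not in the protocol and is assumed to be 1 to 3 visits.

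| Pairs | SD 1 | SD 1.5 | SD 2 | SD 3 |
|---|---|---|---|---|
| 60 | ±0.25 | ±0.38 | ±0.51 | ±0.76 |
| 48 | ±0.28 | ±0.42 | ±0.57 | ±0.85 |
| 42 | ±0.30 | ±0.45 | ±0.60 | ±0.91 |

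That is enough to reveal gross misreporting, though not a small bias.

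**6. A mismatch on data sources.** Section 7.1 lists only prescribing data from linked records among the sources that form the basis of data collection, whereas section 5.3.3 includes consultations.

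**The case against.** The strongest reply is that this asks for an extra analysis and identifies no mistake. Section 6.2 calls the quantitative work exploratory, and an unseen analysis plan could compare visit counts. Section 6.2.6 also goes beyond the listed outcome by naming suitability and appropriateness of completion. Part of this stands: no sections contradict each other on the outcome itself, and nothing forbids the comparison. But the protocol itself sets the outcome for a primary objective and restricts the record comparison in 6.2.6 to opioids. The added terms, without a criterion, do not supply an accuracy check.

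The second reply is that the comparator is imperfect, and this stands in full. A reader might infer that the extracted records would simply reveal forgotten visits. The documents do not support that. The questionnaire's focus is narrower than the records, linked records exist only for consenters, and section 7.1 leaves it unclear whether consultation data, with reason for visit, will reach the analysis. GP records are also not said to verify private care, over-the-counter purchases or work loss, or to capture all secondary care.

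The third reply is that the contrast with objective 4 is not an inconsistency, because morphine equivalent dose is a proposed co-primary outcome and deserves a closer check. That is fair. The contrast shows that the method is already in the plan, not that the two objectives must be treated alike.

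**Conclusion.** The point holds for primary-care contacts. As written, the measures assigned to objective 5 can establish that the questionnaire is returned and filled in, but not that its contact counts are accurate, and data bearing on that are to be extracted. This does not depend on any assumed rate of forgetting.

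A reader might go further and infer that main-trial visit costs will be understated by some stated percentage. The documents give no basis for that: the recall losses of 10% to 40% are illustrative. Nor does the gap alter any decision rule here, since no progression criterion in section 6.5 rests on objective 5. It is an inexpensive improvement that would let the study answer its own objective better.

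The precision of ±0.25 to ±0.76 visits rests on 60 pairs and an assumed SD of 1 to 3. At 42 pairs it widens to between ±0.30 and ±0.91.

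**What to change.** In the objective 5 row of the Study Summary and in section 6.2.6, add a descriptive comparison for primary-care contacts only, among participants who consent to record access:

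- **Pharmacist contacts.** Where the questionnaire asks for them, compare self-reported clinical pharmacist contacts with the PROMPPT appointments already recorded as intervention resource use. No classification by reason is needed.
- **GP and nurse contacts.** Compare self-reported contacts with extracted consultations over the same 3-month window, using the coded reason where available. Where it is not, show all-cause counts as an upper bound only and do not call the gap under-reporting.
- **Reporting.** Give the mean difference with its 95% interval and the distribution of individual differences. Use these with completeness when choosing the main-trial source for primary-care contacts.
- **Consistency.** Align section 7.1 with section 5.3.3 so that consultation data are named as a source.

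The cost is some classification of consultations and matching of dates to the recall window; the receipt stamp on questionnaires (section 7.2) gives an approximate anchor. No new data are collected from participants. The comparison leaves private care, over-the-counter purchases, work loss and most secondary care unchecked, and the report should say so.

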#### STUDY FLOW CHART

# **STUDY GANTT CHART**

ACTIVITY																
Month	Pre	1	2	3	4	5	6	7	8	9	10	11 1	2 13	14	15	16
Project Management Group																
Programme Steering Committee																
Patient Advisory Group Meetings													$\perp$			
Pharmacy Advisory Group Meetings													$\perp$			
Prepare documents for regulatory approval and gaining necessary approvals											$\perp$	$\perp$	丄			
NIHR: CRN GP practice identification and recruitment													$\perp$			
Developing & delivering training for clinical pharmacists (including ongoing support )																
Database development																
Patient recruitment													$\perp$			
Patients invited to arrange PROMPPT appointment																
Initial PROMPPT consultations (approximately n=2 per practice observed/audio-recorded)																
Follow-up PROMPPT appointments (as needed)																
Participants complete 3-month follow-up questionnaire																
Semi-structured interviews (Patients and HCP's)																
Quantitative data entry and analysis																
Qualitative data analysis																
Refine PROMPPT Intervention and trial processes for a main trial																
Finalised PROMPPT intervention																

### 1. BACKGROUND

Persistent pain, defined as long-term pain not caused by cancer, affects almost half the UK adult population, with 10-14% (around 8 million adults) reporting that persistent pain causes moderate or severe interference with life. Two-thirds of people with persistent pain are treated with prescribed analgesics and, of these, 62% are prescribed opioid (morphine-like) analgesics. Opioid prescribing for persistent pain has increased, with a trend towards prescribing stronger long-acting opioids and earlier escalation from 'weak' (e.g. codeine) to 'strong' opioids (e.g. morphine). In UK primary care, prescribing almost doubled for 'weak' opioids and rose almost six-fold for 'strong' opioids between 2005-2012, with much of this prescribing being for patients with unspecified non-cancer pain. Prescribing of the most commonly used 'strong' opioids (morphine, oxycodone, fentanyl, buprenorphine) increased by 466% between 2001 and 2010, with most (87.8%) prescribed for non-cancer pain.

Evidence for long-term effectiveness of opioids for people with persistent pain is limited. 6-8 The majority of people living with persistent pain do not obtain useful pain relief from opioids and they are frequently associated with side-effects which can worsen quality of life, including constipation, nausea, dizziness, sedation and confusion. 6,7,10 People with persistent pain who take opioids are more likely to report worse pain, poorer self-rated health, and lower quality of life than people with persistent pain who do not take opioids. 11,12 These data suggest that, for many people with persistent pain, opioid therapy does not fulfill the key goals of treatment, namely pain relief, improved functioning and improved quality of life and. Opioid therapy is also associated with increased risk of serious harm including overdose, addiction, fractures and myocardial infarction. 13-15 Furthermore, studies of gradual reduction of long-term opioids in the context of multidisciplinary pain management programmes report that, overall, patients do not experience worse pain and may notice improved function and quality of life. 16

It seems, therefore, that opioids are prescribed more often and for longer than would be expected given the evidence for their effectiveness for persistent pain. Most long-term opioid prescribing occurs in primary care, where most persistent pain is managed. GPs report low satisfaction with care they provide for patients with persistent pain  and, whilst 75% report concerns about opioid-related harm, 50% of GPs perceive no alternative to prescribing opioids for some patients. 

#### 2. RATIONALE

Best practice guidelines  recommend that opioids should be reviewed within four weeks of starting opioid treatment. Once a stable opioid regimen is reached, it is recommended that opioids should be reviewed face to face at least 6 monthly, and more often if there are concerns. Structured review is recommended, taking into account evidence of effectiveness, including functional improvement / progress towards treatment goals, side-effects and evidence of problematic use. Supporting patients to taper and stop opioids is recommended if treatment goals are not met . However, implementation of opioid guideline recommendations is low.  Lack of time and resources are potential barriers to guideline-concordant care,  and the available time in routine GP appointments offers limited opportunity to undertake a comprehensive face-to-face review.

To address challenges facing primary care, a recent report recommends adopting a multidisciplinary model and increasing the role of clinical pharmacists working within GP practices in managing patients on long-term medicines. An expansion in the clinical pharmacist workforce in UK primary care is underway, with clinical practice pharmacists being a key component of the evolving Primary Care Networks (PCNs). These practice clinical pharmacists will see patients in face-to-face consultations in GP surgeries and will be trained as independent prescribers. Practice pharmacists do not dispense medicines and patients will still collect their medicines from the community pharmacy in the usual way. There is considerable variation in the roles adopted by clinical pharmacists in GP practices and research is needed to determine the most clinically and cost-effective ways to utilise this new primary care resource. One emerging role for clinical practice pharmacists is reviewing patients with polypharmacy and complex medicines regimens. Given that increasing polypharmacy is associated with incremental increases in long-term and stronger opioid prescribing,  clinical practice pharmacists are ideally placed to take a proactive role in reviewing and managing patients on long-term opioids, but there is currently no evidence about how they should do this or whether it would be clinically or cost-effective.

Evidence supporting interventions to reduce opioid use is sparse. Recent Cochrane reviews found the need for further, larger, RCTs of theoretically grounded behaviour-change interventions focussing on reducing opioids in the context of persistent pain.

This study is part of a 5-year research programme comprising three linked workstreams to develop and test a clinical pharmacist-led primary care intervention (PROMPPT) and an associated clinical pharmacist training package which aim to reduce opioid use for people with persistent pain (where appropriate) and support self-management for those with persistent pain in primary care.

In workstream 1 (WS1), we used a person-based approach, combined with best practice guidance, theory (on behaviour change and normalisation of health care interventions) and stakeholder engagement, to develop the PROMPPT pain management review and clinical pharmacist training package.

This protocol describes workstream 2 (WS2), a non-randomised feasibility study and nested mixed methods process evaluation, which will inform refinement of the PROMPPT pain management review, training package and the design of the proposed main trial design. In workstream 3 a multicentre cluster randomised controlled trial (cluster RCT) will test the clinical and cost-effectiveness of providing the PROMPPT pain management review in reducing prescribed opioid use, without increasing pain/pain –related interference, when compared with usual primary care review of patients prescribed long-term opioids.

